Further, little attention has been paid to how specific subgroups of people in prison (such as people with mental health problems) fare in terms of their physical health. Features of the prison system can simultaneously exacerbate mental distress and impede access to healthcare and support, limit opportunities for self-care and can lead to self-harm and (mis)use of prescribed and non-prescribed drugs. People with mental health problems have greater prevalence of obesity, cardiovascular disease, chronic kidney disease, and polypharmacy, which complicate physical health management, and those prescribed atypical antipsychotics often have poorer glycaemic control making people in prison an especially vulnerable, underserved group.

We have previously developed and applied a set of 'high impact' quality indicators for primary care, based on criteria including: burden of illness (e.g. prevalence, severity), potential for significant patient benefit (e.g. longevity, quality of life), scope for improvement upon current levels of achievement, and the feasibility of measurement using routinely collected data [23]. Other indicators are available but not yet routinely applied to prison populations, including primary care quality indicators for people with serious mental illness [24]. We are now in a position to build upon these, understand variations in prison primary care, and initiate strategies to improve prisoner healthcare and outcomes. For example, the detection and management of hypertension reduces avoidable mortality and morbidity [25]; there is scope for improving upon current management in primary care, whereby just over two-thirds of people with hypertension are achieving treatment goals [26]. The detection and treatment gaps in the prison population are unknown, thereby undermining priority setting and planning to reduce avoidable cardiovascular events in this population.

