### 6.4 SAMPLING AND SETTING CONTEXT

The data will be extracted for those prisons where Spectrum CIC provide primary care services. This will be done via SystmOne Prison, the IT system that currently holds the data

for prison-based health care for all prisons in England. Spectrum CIC are currently responsible for primary healthcare in 12 adult prisons: three category A (high security); four category B (remand); five category C (training); and one category D (open). These collectively have a capacity of approximately 8,560 prisoners in total (range 280 to 1,350).

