#### 6.6 DATA ANALYSIS

#### **ANALYSIS**

#### We will determine:

- percentage achievement of quality indicators for the prisoner population as a whole
- comparisons of percentage achievement by:
  - prison type
  - sentence duration
  - age
  - gender
  - other relevant characteristics
- whether there are systematic differences in quality for these variables

One hypothesis is that long stay prisoners are likely to have relevant quality indicators recorded in prison, whilst those serving shorter sentences (e.g. <3 months) may be overlooked or even not apply in the time they are in prison. Exploring prisoner characteristics, such as age, is particular pertinent with the growing number of elderly prisoners (both in absolute terms and as a proportion of the prison population); and the accompanying poorer health of aging prisoners [35].

An initial descriptive and Bayesian analysis will be undertaken and then multi-level logistic regression modelling and a latent variable analysis. The initial analysis will provide the necessary information (i.e. achievement numbers, rates and levels) to assess whether further analysis is appropriate (see credibility and sense checking section below for further details). Multi-level logistic regression models will identify the factors that are associated with

achievement of the quality indicators. These types of models can appropriately account for the potential correlations between outcomes at multiple time-points and between-prison variation. The initial descriptive and Bayesian analysis will provide contextual background to understand achievement levels for the quality indicators across prisons. These between-prison differences will need to be accounted for, while exploring variations in attainment. With likely strong associations between the different quality indicators, latent variable models will be developed to identify factors common across all indicators. This unifying model will explore which factors are associated with quality in care in prisons as measured by all these indicators.

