#### 6.7 SAMPLE SIZE CONSIDERATIONS

This WP aims to explore variations in the quality of primary care provision for prisoners. As such a formal sample size calculation is not appropriate as the aim is to describe the current provision. However a consideration of the characteristics of the study population shows the potential to explore the variation in prisoner groups and prisons. Taking a potential health condition with a relatively low prevalence - mental illnesses (schizophrenia, bipolar affective disorder and other psychoses), we would expect 77 prisoners to be diagnosed from the 11 prisons (0.9% prevalence based on QoF for England 2015-16). This expected number of prisoners diagnosed does not take into account the probable higher prevalence in prisoners nor the throughput of prisoners which would increase the sample population over the 3 years and so those diagnosed. For example, as a remand prison Durham has on average 60% of prisoners transferred within 50 days. If we use the lowest achievement (49%) of the QoF indicator 'The percentage of patients with a comprehensive care plan documented in the record, in the preceding 12 months', we would expect 38 of the 77 prisoners to achieve the QoF indicator. If we use the rule of thumb that logistic models should be used with a minimum of 10 events per factor/predictor variable, based on simulation studies [37], then we would be able to explore approximately three factors simultaneously as to whether they are associated with achievement of the indicator. Furthermore, using multi-levels and latent models, will likely result in the number of records required to be reduced and allow more factors to be explored with the same number of records. Therefore even with the lowest prevalence of both the condition and achievement of indicator, based on community data, we have potentially a more than sufficient study population size to explore the factors associated with variation in quality indicators.

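### Section 6.7 treats 49% achievement as the worst case for the 10-events rule, but the rule is limited by the smaller outcome group, so 49% is nearly the most favourable level

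*Protocol*

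**What the plan says.** Protocol section 6.7 states that no formal sample size calculation is appropriate, then gives an illustration and draws a conclusion about adequacy from it.

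- Number with the condition: "we would expect 77 prisoners to be diagnosed from the 11 prisons (0.9% prevalence based on QoF for England 2015-16".
- Achievement: "If we use the lowest achievement (49%) of the QoF indicator", which leads to "we would expect 38 of the 77 prisoners to achieve the QoF indicator".
- Rule: "logistic models should be used with a minimum of 10 events per factor/predictor variable", from which it allows about three factors.
- Conclusion: the population is judged potentially ample for exploring factors "even with the lowest prevalence of both the condition and achievement of indicator".

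The section adds that 77 leaves out the probably higher prevalence in prison and the turnover of prisoners over three years. It never mentions the prisoners who do not achieve the indicator.

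Section 6.6 says that the initial descriptive and Bayesian results will supply "achievement numbers, rates and levels) to assess whether further analysis is appropriate". Section 7A.5 repeats the WP3 modelling approach in the three WP5 mental health subgroups.

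**The concern.** The conclusion in 6.7 has the form of a stress test: if the sample copes with the lowest achievement, it copes with the rest. That holds only if support for a model rises with achievement. It does so up to 50% and falls beyond it.

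If 49% is the lowest level, as 6.7 says, other levels lie above it. Past 51% they support fewer factors than the example, while a count of achievers goes on rising. The two counts therefore move in opposite directions over the range where most of the indicators would sit.

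What is at stake is an adequacy statement that readers will rely on, and the reliability of odds ratios for well-achieved indicators if someone sizes a model by counting achievers. WP3 associations inform the WP4 priority setting (section 7.4, step a), which looks at groups of prisoners with lower achievement.

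**Working it through.** **Inputs.** Section 6.4 gives a "capacity of approximately 8,560 prisoners in total". Section 6.7 gives 0.9% prevalence, 49% achievement and 10 events per factor. Section 2 gives one higher achievement level, for community hypertension: "just over two-thirds of people with hypertension are achieving treatment goals", taken here as 67%. The levels 80%, 90% and 95% are not in the protocol; they are assumptions chosen to show a range.

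**The plan's own figures.**
- 8,560 × 0.009 = 77.04, so 77.
- 77 × 0.49 = 37.7, so 38 achievers; 77 − 38 = 39 non-achievers.
- 38 / 10 = 3.8, so three whole factors.

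All three figures reproduce. At 49% the smaller group also gives three whole factors, so the example itself is sound.

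**Which count limits the model.** If logit P(achieved) = xβ, then logit P(not achieved) = −xβ. The likelihood, fit and standard errors are the same and only the signs change. The number of factors supported cannot depend on which outcome is called the event, so the limit is

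factors = n × min(p, 1 − p) / 10.

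This is largest at p = 0.50, where it is 77 × 0.50 / 10 = 3.85. At 49% it is 77 × 0.49 / 10 = 3.77, which is 98% of the maximum.

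**Over a range of achievement, n = 77.** The last column is 30 / min(p, 1 − p), the number of eligible prisoners needed for three factors.

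| Achievement | Achievers / 10 | Smaller group | Smaller group / 10 | n for three factors |
|---|---|---|---|---|
| 49% (section 6.7) | 3.8 | 37.7 | 3.8 | 62 |
| 67% (section 2, illustration) | 5.2 | 25.4 | 2.5 | 91 |
| 80% (assumed) | 6.2 | 15.4 | 1.5 | 150 |
| 90% (assumed) | 6.9 | 7.7 | 0.8 | 300 |
| 95% (assumed) | 7.3 | 3.9 | 0.4 | 600 |

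At 90%, for example, a count of achievers would allow six whole factors. Those six would rest on 7.7 / 6 = 1.3 limiting outcomes each.

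Below 50% the achievers are the smaller group and the plan's count is the right one: 30% achievement gives 77 × 0.30 / 10 = 2.3. Support falls in both directions from 50%, and 49% tests neither.

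**The case against.** The strongest reply is that 6.7 is an illustration and not a design rule. It disclaims a formal calculation, fixes no number of factors for any indicator, and gets its own example right. That stands as far as it goes. But the section still ends with a general adequacy claim, and that claim is what fails.

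Second, 77 is acknowledged to be an undercount, and commoner conditions will have many more eligible prisoners. This also stands. Pairing 67% with 77 mixes a hypertension level with a severe mental illness count, so that row is illustrative only, and at 67% three factors need just 91 people. A larger n eases the shortage but does not turn 49% into a worst case.

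Third, 6.7 says that multi-level and latent models will lower the number of records needed. It gives no figure, and the argument does not change which outcome group is the limiting one.

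A reader might infer that the protocol will over-model high-achievement indicators, because 6.6 makes modelling depend on achievement results. The text does not support that. Section 6.6 refers to numbers, rates and levels together and points to the credibility checks, not to 6.7, so a very high rate would be visible at that stage. Nothing makes the achiever count the criterion for modelling.

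Finally, the current version describes the WP3 data as already extracted (section 7A.4) and cites WP3 findings (section 7A.5). A correction therefore bears mainly on how WP3 results are reported and on the WP5 models.

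**Conclusion.** The point holds as an error of reasoning in a stated adequacy claim. The arithmetic in 6.7 is correct; the worst-case label is not, because 49% gives 98% of the most favourable value that 77 prisoners can provide. This rests only on the symmetry of the logistic model and on the protocol's own rule of 10, not on the cited simulation study.

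The size depends on achievement and on the number eligible. Taking 77 as given, support falls below three factors by 67% and below one by 90%. The levels from 80% upwards are assumptions, and the true number eligible may be well above 77. The shortfall for any particular indicator is therefore unknown. Over-modelling is a risk if the 6.7 count is carried into the modelling decision; the protocol does not say that it will be.

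**What to change.** In section 6.7:
- Define events as the smaller of achieved and not achieved.
- Withdraw the sentence that presents the lowest achievement as the hardest case.
- State the factors supported, or the number of eligible prisoners needed, over a range of achievement levels labelled as assumptions. The table above would serve, recalculated with the actual number eligible where that is now known.

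When judging under section 6.6 whether multivariable modelling is appropriate, use the same smaller-group count, and do so for the WP5 subgroup models that repeat the WP3 approach. Report indicators that fall below it descriptively with intervals, or with a penalised model. For WP3 models already fitted, give the smaller-group count beside each so that readers can judge its stability.

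The cost is a few lines of text and no new data. The stated adequacy becomes less favourable, and some high-achievement indicators will stay descriptive.

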# 7 WORK PACKAGE 4: IDENTIFICATION OF INTERVENTIONS TO IMPROVE PRISONER HEALTH

# 7.1 OBJECTIVE

To integrate the findings from work packages one, two and three within a stakeholder consensus process in order to prioritise and enhance quality improvement interventions which can be monitored by our set of quality indicators.

#### 7.2 TIMESCALE

Months 22-25 (May-Aug 2021), synthesis of work package one, two and three findings and consensus panel preparation

Months 26-29 (Sep-Dec 2021), convene x3 stakeholder panels

Months 30-33 (Jan-Apr 2022), write up

#### 7.3 PARTICIPANTS

As for WPI, the consensus panel of up to 11 members will be drawn from key stakeholders involved in commissioning and delivering primary care, along with prisoners and their advocates. These 11 people do not necessarily need to be the same as those who participated in WPI. We will seek consensus on key areas for intervention, and on what kinds of quality improvement interventions need to be enhanced or adopted to improve quality of care.

#### 7.4 METHOD

We will share our findings from WPs I-3, with the panel and take them through the following steps:

- a. Review findings from WP3 to identify priorities for improvement based each indicator such as low performance or groups of prisoners associated with lower achievement of indicators, (e.g. older people, longer or shorter term prisoners).
- b. Consider findings from WP2 to understand barriers to and enablers of good quality of care, considering levers for change at individual, team, organisational and wider system levels.

- c. A briefing summarising the range of approaches (interventions) potentially available to support the implementation of quality indicators, drawn from a broad overview of systematic reviews (or most recent updates then available).
- d. Mapping of implementation interventions to identified barriers and enablers. Examples are as follows: (i) if clinical staff or teams are unaware of their poorer performance relative to other clinical staff and teams, then audit and feedback comparing data on performance can help identify erroneous perceptions and use social comparisons and goal setting to motivate change; (ii) if clinical staff under pressure within time-limited consultations are unable to recall key information about patients or knowledge of care pathways, then specifically targeted computerised prompts and templates can support decision-making and action; or (iii) if prisoners with long term conditions, such as asthma, do not consistently understand the importance and consequences of requesting or taking preventive treatment (or how to do so), targeted patient information and instruction from clinical staff can support treatment adherence. These examples illustrate types of approaches requiring planning and action at individual, team, organisational and system levels.
- e. Application of APEASE criteria (affordability, practicability, effectiveness, acceptability, safety and equity) [38]. For each intervention, we need to consider likely adaptability to and sustainability within the prison healthcare environment.

We will plan three consecutive, half day panel meetings to allow sufficient time and reflection to work through these five sets of considerations.

#### 7.5 ANALYSIS

We will use ratings by panellists for steps A (priority setting) and E (appraising applicability of candidate interventions). As for WPI, for each of these panellists will independently rate each priority or feature of an intervention (e.g. affordability) on a 1-9 scale, where scores of 'I' indicates the strongest disagreement and scores of '9' indicate strongest agreement. We will collate the scores for each and feedback the median and range scores to all participants for a face-to-face discussion. We will discuss ratings, focusing on those with maximal discordance, defined as at least three panellists rating a priority or intervention feature 1–3

and at least three rating 7–9. Participants will then independently rate each item again. This process offers a relatively transparent and inclusive approach to select priorities and interventions, so that those with the highest aggregate scores are carried forward. Written notes will be taken by participating members of the research team during and after workshops and these, together with any materials developed by participants as part of their evaluation, will be included in the analysis. Some sections of the workshops (with participants' permission) may be recorded and transcribed to allow us to check and review any key decisions and recommendations. Using the findings from the workshops a prioritised list of quality indicators and a suite of implementation interventions relevant to the prison healthcare setting will be identified, likely to be based around the commissioning of prison healthcare, development and sharing of patient records, and delivery of prison-based primary care.

# 7A WORK PACKAGE 5: MENTAL HEALTH WORKSTREAM (QUALITATIVE AND QUANTITATIVE ANALYSES OF DATA COLLECTED IN WP2 AND WP3)

# 7A.I OBJECTIVE

To report on outcomes for prisoners with mental health problems by exploring perceptions of the quality of mental health care and identifying barriers and enablers of good mental health in prison through thematic analysis of qualitative data collected in WP2; and by conducting statistical analyses of routinely collected data obtained in WP3 to assess the quality of physical health care provided to mental health subgroups.

#### 7A.2 TIMESCALE

Months 37-39 (May 22-Jul 22)

#### 7A.3 DESIGN

#### QUALITATIVE DESIGN

We will undertake a qualitative analysis of the qualitative data collected in WP2, focusing on the receipt and provision of mental health care.

QUANTITATIVE DESIGN

We will statistically analyse routinely collected data obtained in WP3. We will identify and describe three mental health subgroups and explore variations in the quality of their physical care as compared to the rest of the prison population.

#### 7A.4 SAMPLING AND SETTING

Both our qualitative and quantitative data were collected in the Clinical Research Network regions with the highest prevalence of mental health conditions (Greater Manchester, North west Coast, North East and North Cumbria).

#### QUALITATIVE DATA

The qualitative data was collected from 23 people who had lived in prison and 21 prison healthcare staff. The entire dataset will be included in the mental health focused analysis.

#### QUANTITATIVE DATA

The quantitative data was extracted from all prison healthcare records held at 13 prisons for the years 2017-2020. Data will be analysed for three subgroups:

The proportion of the population across 13 prisons:

- (i) with any mental health diagnosis
- (ii) prescribed any psychotropic drugs
- (iii) with any mental health diagnosis NOT prescribed a psychotropic

### 7A.5 ANALYSIS

#### QUALITATIVE ANALYSIS

We will conduct an inductive, reflexive thematic analysis (Braun & Clarke, 2019) of the entire qualitative dataset collected in WP2. Analyses conducted for WP2 have already identified data relating to experiences of poor mental health, barriers to achieving good mental health and strategies for overcoming these barriers. This additional analysis will involve:

- Re-reading the entire dataset (44 transcripts)
- Conducting focused coding around the broad topic of mental health and wellbeing
- Identification of themes and sub-themes

#### QUANTITATIVE ANALYSIS

#### We will determine:

- percentage achievement of quality indicators for the three mental health subgroups
- comparisons of percentage achievement in the wider prison population by:
  - prison type
  - sentence duration
  - age
  - gender
  - other relevant characteristics
- whether there are systematic differences in quality for these variables

One hypothesis is that achievement for the indicators will be lower for these subgroups compared to the rest of the prison population. Findings from analyses undertaken in WP3 suggests variations across prisons, and that sentence length and other individual characteristics (such as age and gender) have the potential to affect achievement but we do not know if this will hold true for these three subgroups whose demographic may differ from the wider population.

We will repeat the approach taken in WP3 by performing an initial descriptive and Bayesian analysis, followed by multi-level logistic regression modelling to identify factors associated with achievement of the quality indicators.

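### WP5 asks whether WP3's associations also hold in the mental health subgroups, but the only method it states includes no comparison of associations between a subgroup and the rest

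*Protocol*

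**What the plan says.** Protocol section 7A.3 (quantitative design) sets out to describe three mental health subgroups and "explore variations in the quality of their physical care as compared to the rest of the prison population". Section 7A.4 defines them as people with any mental health diagnosis, people prescribed any psychotropic, and people "with any mental health diagnosis NOT prescribed a psychotropic". The third lies inside the first. No sizes are given.

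Section 7A.5 (quantitative analysis) then contains two different questions:

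- One about level: "One hypothesis is that achievement for the indicators will be lower for these subgroups compared to the rest of the prison population".
- One about associations. After noting that prison, sentence length, age and gender may affect achievement in WP3, it adds "but we do not know if this will hold true for these three subgroups whose demographic may differ from the wider population".

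The method follows: "We will repeat the approach taken in WP3 by performing an initial descriptive and Bayesian analysis, followed by multi-level logistic regression modelling". The stated aim of that modelling is to find which factors are linked to achievement. The approach being repeated is in section 6.6: "Multi-level logistic regression models will identify the factors that are associated with" achievement, after a descriptive and Bayesian stage.

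**The concern.** The question about level is a main effect: is achievement lower in a subgroup than in the rest? The question about associations is different. It asks whether, say, the odds ratio for sentence duration is the same in people with a mental health diagnosis as in everyone else. Answering it needs a contrast between two odds ratios, and models that list associated factors do not supply one.

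If the same models are rerun and the resulting factors set beside those of WP3, a factor may fail to appear in a subgroup only because the subgroup holds less information. Agreement would also be weaker support than it looks, because the WP3 population contains the subgroups.

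WP5 could then report that a known correlate of poor care does not apply to people with mental health problems when the data show no such thing. Two papers are planned from WP5 (section 8.3), and study findings are meant to reach commissioners and providers (section 8.1).

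**Working it through.** **The plan's own figures.** There is no figure for WP5. The WP3 illustration in section 6.7 reproduces: 0.009 × 8,560 = 77.04, stated as 77; 0.49 × 77 = 37.7, stated as 38; 38 / 10 = 3.8, stated as about three factors. The 8,560 is the capacity in section 6.4. The 77 people are not a WP5 subgroup.

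**Does any stated step compare associations?**

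- Section 6.6, descriptive stage: achievement overall and by characteristic.
- Section 6.6, Bayesian stage: achievement levels across prisons, and false negative and false positive rates.
- Section 6.6, regression: factors associated with achievement, allowing for prison and repeated time-points.
- Section 7A.5: subgroup percentages, comparisons in the wider population by characteristic, then a repeat of the above.

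None names an interaction, a contrast of coefficients, or a rule for deciding that an association holds.

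**Illustration 1: subgroup against the whole WP3 population.** Assumptions, none from the protocol: the true effect is the same in everyone, each record carries equal information, and tests are two-sided at 5%. Let z be the expected test statistic in WP3 and f the subgroup's share of records. In the subgroup the expected statistic is z√f. Because the subgroup is part of WP3, the two statistics correlate at √f. The chance of significance in WP3 but not in the subgroup is P(Z_WP3 > 1.96 and Z_sub < 1.96), from a bivariate normal with means z and z√f and correlation √f.

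At z = 3.24 power in WP3 is 90%. For f = 0.5 the subgroup mean is 3.24 × 0.707 = 2.29, so subgroup power is 63.0%. Both are significant with probability 61.8%. The discordant chance is 90.0% − 61.8% = 28.2%.

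| Expected z in WP3 | f = 50% | f = 25% | f = 10% |
|---|---|---|---|
| 3.24 | 28.2% | 54.1% | 73.1% |
| 4 | 17.5% | 46.5% | 73.7% |
| 6 | 1.1% | 14.9% | 52.5% |
| 8 | 0.0% | 2.1% | 28.4% |

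**Illustration 2: subgroup against the rest.** Assumptions: 8,560 people, a binary factor split 50/50, 49% achievement in the reference level, no clustering, and the same odds ratio in both groups. The groups are now independent, so the chance of significance in the rest only is power(rest) × (1 − power(subgroup)). For OR 1.3 and a 10% share this is 1.000 × (1 − 0.481) = 0.519.

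| True OR in both groups | 50% | 30% | 20% | 10% |
|---|---|---|---|---|
| 1.2 | 13% | 34% | 51% | 72% |
| 1.3 | 1% | 9% | 23% | 52% |
| 1.5 | 0% | 0.1% | 1% | 16% |

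A direct Wald test of the difference between the two log odds ratios was simulated with 20,000 replicates per setting, over five settings. It declared a false difference in 4.8% to 5.2% of replicates, as it should.

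Both illustrations ignore clustering by prison and repeated measures, which would reduce precision further.

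**The case against.** The protocol nowhere says that models will be fitted separately in each subgroup, that lists of significant factors will be compared, or that an association fails to hold when p exceeds 0.05. A reader might infer that WP5 is bound to produce false differences, or that its conclusions will turn on sample size alone. The text does not support either reading. Repeating the approach could mean a joint model, and section 7A.3 does compare the subgroups with the rest. This stands. Even so, a joint model with subgroup only as a covariate would answer the question about level and not the one about associations.

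A second objection is that interaction terms belong in a statistical analysis plan, which is not shown and may contain them. This has force. But the protocol states both the question and the method, and they do not match, which is more than an omitted detail.

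Third, the work is exploratory, and the sentence about associations may be only motivation. Describing associations within each subgroup, with intervals, is legitimate. It still does not show whether they differ from those elsewhere.

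Fourth, the magnitude depends on assumed inputs. A reader might quote subgroup non-significance alone at z = 3.24 (37%, 63% and 83% for shares of 50%, 25% and 10%) as the error rate. That overstates it, because the misreading also needs significance in WP3. The subgroup definitions are broad and three years' throughput enlarges the population, so the risk may be small for strong associations.

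**Conclusion.** The mismatch between question and method stands, at the level of something that should be changed. Section 7A.5 raises effect modification and states only models that identify associated factors.

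The consequence is conditional: if the question is judged from repeated models, a smaller subgroup can seem to have different drivers through lower precision alone. On the stated assumptions the size runs from near zero (large subgroup, strong effect) to about 73% per factor and subgroup (10% share, z = 3.24). No single figure can be fixed, because the protocol gives neither subgroup sizes nor effect sizes. The risk is greatest for weak associations, for the untreated subgroup nested in the diagnosed one, and for indicators that apply only to people with a particular condition.

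**What to change.** In section 7A.5, keep the descriptive work and the comparison of achievement levels, and add a paragraph for the question about associations:

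- For each indicator and each subgroup definition (subgroup versus rest), fit one multi-level logistic model to the full WP3 dataset.
- Include subgroup-by-factor interactions for prison type, sentence duration, age and gender.
- Report each interaction as a ratio of odds ratios with a 95% interval, together with the subgroup-specific effects from the same model.
- State that an association will be called different only on the interaction, not because it is significant in one set and not in the other. A wide interval should be reported as uncertainty, not as evidence that the association is the same.

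Separate models per definition are needed because the third subgroup is nested in the first and the second can overlap the first.

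The cost is one paragraph and extra model terms on data already held. The downside is that interaction intervals will be wide, and indicators with few eligible people may support only some of the interactions. Which ones are kept in that case should be decided before the models are run.
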